Participants must (i) be able to provide informed consent, (ii) be able to stand and walk independently without an assistive device, (iii) not self-report diagnosis of a neurological disease, and (iv) not a self-report diagnosis of any limb disabilities, injuries, or disease.

10. Exclusion Criteria

What are the specific exclusion criteria?

N/A

11. Pregnancy and Contraception Requirements

A. Are women of child bearing potential (WOCBP) included in this research?

Yes

a. Are there any specific contraception requirements for subjects?

No

1. Provide justification for absence of contraception requirements

◆ There are no interventions that are likely to be of risk to a fetus

Investigational drug(s) is (are) not systemically absorbed

Investigational drug(s) is (are) systemically absorbed, but there is no evidence from human studies, or from clinical experience, that there is risk to a fetus

Other

B. Are pregnant women included in this research?

No

1. Provide justification for excluding pregnant women

Investigational drug(s) is (are) absorbed systemically, and there is evidence from animal or human studies, or from clinical experience, that there is risk to a fetus **OR** investigational drug(s) is (are) absorbed systemically, and there is a well-understood mechanism of action that may result in risk to a fetus

Intervention includes a procedure expected to be of risk to a fetus (eg, exposure to ionizing radiation, maximal exercise test)

Research is not relevant to pregnant women (e.g. disease or condition rarely encountered in

pregnant women)

Knowledge being sought in the research is already available for pregnant women or will be obtained from another ongoing study

A separate study in pregnant women is warranted and preferable

♦ Physiology of pregnancy precludes generalization to other populations

Other - explain

2. Describe how pregnancy status will be assessed (eg, self-report, urine pregnancy test, blood pregnancy test) and the frequency of monitoring during participation in the research.

Self-report

3. Describe the plan should a female subject, or the partner of a male subject, become pregnant while research interventions are on-going (or during the period that contraception is required following the completion of the intervention).

Subjects will be recruited for one data collection session lasting no more than 3 hours.

Therefore, contraception or pregnancy status will unlikely change during the described protocols.

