C. Are breast feeding women excluded in this research?

No

Provide justification for the inclusion or exclusion of breast feeding women.

There is no added danger to breast feeding women during sighted or blindfolded walking sessions in this protocol.

METHODS AND PROCEDURES (NON-THERAPEUTIC)

12. Methods and Procedures Applied to Human Subjects

A. Describe the research plan, including all procedures, interventions, evaluations and tests. If subjects will be randomized to a specific intervention, the randomization plan should be explained.

Tasks, procedure, and instructions to the participant

Participants will be tested in an indoor laboratory in the Biomechanics Research Building at the University of Nebraska at Omaha. After taking informed consent, participants will be fitted with retroreflective markers and an eye tracker (see below). In Aim 1, participants will maintain an upright stance on a stable surface a pair of force plates in one condition and perform the Trail Making Test while maintaining an upright stance in the other. The Trail Making Task will be presented on a projector screen and involve drawing a trail through jumbled numbers. In Aim 2, participants will maintain an upright stance on an unstable

surface a balance board placed on the force plates in one condition and perform the Trail Making Test while maintaining an upright stance on the same unstable surface in the other. Each trial is expected to last about seven-eight minutes and will be repeated if the participants lost balance at any time between the trial for a maximum of two repetitions. Participants will be subjected to three trials of each of the four conditions in a single experimental session lasting 120 mins. The order of the 12 trials will be randomized for each participant.

Balance board

Balance boards, which include rocker boards and wobble boards, are a fitness tool people can stand on while performing exercises to help improve balance and posture, aid in rehabilitation, prevent lower body injuries, and increase core strength, among other benefits. We will use a lateral balance board as show in the attached picture.

Posturography

Participants will stand on dual 40×60 cm floor-embedded force plates (400600HPS, AMTI Inc., Watertown, MA) with one foot on each force plate. Participants will be given no additional instructions that can impose artificial constraints on the posture. Ground reaction forces will be recorded at 200 Hz.

Motion tracking

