Participants will be outfitted with a form-fitting compression suit, lab-provided athletic shoes in their size, and a full-body, 79-marker retroreflective marker set before the study. Marker trajectories in 3D will be collected at 200 Hz using a 17-camera motion capture system (Motion Analysis Corporation, Santa Rosa, CA). An RGB camera will record the laser pointer traces on the projector screen. A wireless receiver will be connected to the motion capture system to track eye movements in synchrony with the kinematic data.

Combining eye tracking and motion capture

Participants will wear an eye tracker (100 Hz, Glasses 2, Tobii, Stockholm, Sweden). Before data collection, participants will look at a calibration matrix projected on the screen with calibration marks at known locations. The pixel coordinates of calibration marks will be used to transform the gaze data into the frame of reference of the kinematic data from pixels to millimeters. At each subsequent frame, gaze data will be translated and rotated according to the motion capture system's 6-DoF measurements of head position. Eye tracking will provide a rich resource for pilot analyses of visual exploration during the suprapostural task. Primarily it would allow us to make better contact between the movement dynamics and existing theories of visual cognition. Secondarily, it would inform subsequent experimental designs; for example, we might experimentally manipulate the distance between visual targets within or beyond the comfortable, self-selected ranges.

B. Are all of the procedures, interventions, evaluations and tests being performed solely for research purposes?

Yes

C. Describe briefly the statistical methods used to analyze the data (or reference the appropriate section of the detailed protocol or grant).

Pre-processing of posturography and motion-tracking data

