Center of Pressure (CoP) planar Euclidean displacement (PED) series: The ground reaction forces recorded from the two force plates will be combined to yield a 2D CoP series, describing the CoP position along the participants anterior-posterior and medial-lateral axes. A 1D CoP PED series will be obtained for each 3D CoP series, describing CoP displacement along the body's transverse plane. Center of Mass (CoM) spatial Euclidean displacement (SED) series: The bodily CoMs position will be estimated by submitting segment lengths of the head, trunk, pelvis, left and right hand, forearm, upper arm, thigh, shank, and foot to the equations from Zatsiorsky and Seluyanov (Zatsiorsky and Seluyanov, 1985), yielding a 3D series describing CoM position along the participants anterior-posterior, medial-lateral, and superior-inferior axes. A 1D CoM SED series will be obtained for each CoM series, describing CoM displacement in 3D. Marker SED series: Motion tracking of each reflective marker will yield a 3D series describing its position along the participants medial-lateral, anterior-posterior, and superior-inferior axes. A one-dimensional SED series will be obtained for each marker, describing the displacement of that marker in 3D.

Mapping gaze to the TMT stimulus

The L and R eyes' gaze data will be independently recorded, and for analytical purposes, we will compute the average gaze location between the two eyes for each time point. The transformation of all gaze data will make it relative to the screen. The X and Y coordinates of the gaze position, the timestamp, and the matching world-camera video frame number will be included for each sample in the eye-tracking data file (normalized w.r.t. the world-camera frame dimensions).

Assessing multifractality due to nonlinearity

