Multifractality refers to blending processes across different timescales, producing emergent structures. Multifractal spectrum width will be estimated using Chhabra and Jensens (1989) direct method. A non-zero width will indicate interactions in component processes producing rapidly changing periods of variability, such as small and large changes in fluctuations. To identify whether a nonzero width reflects multifractality due to nonlinearity, the multifractal spectral width for the original series will be compared to those for 32 Iterated Amplitude Adjusted Fourier Transform (IAAFT) surrogates (Ihlen, 2012; Schreiber and Schmitz, 1996). IAAFT randomizes original values time-symmetrically around the autoregressive structure, generating surrogates that randomize phase ordering of the original series spectral

amplitudes while preserving linear temporal correlations. The one-sample t-statistic takes the subtractive difference between the multifractal spectrum widths for the original series and 32 surrogates, dividing by the standard error of the spectrum width for the 32 surrogates. The greater the value of the t-statistic, the greater the multifractality in the original series due to nonlinear as opposed to linear sources.

Network modeling of multiplicative interactions

Vector autoregression (VAR) analysis will be used to model multiplicative interactions across the CoP, CoM, and 79 markers, represented in the model as (CoP, CoM, M1, M2, ..., M79). VAR captures interdependencies amongst concurrent series and will model the effects of t-statistic across anatomical locations in subsequent segments. VAR will yield a temporal trajectory of weights for each combination, defining a directional weighted musculoskeletal network for each participant and task condition. These functional networks will be transformed into binary networks to compare with the anatomical network.

Thresholding the weights using a single, unique threshold value corresponding to the percolation threshold (Esfahlani and Sayama, 2018) will yield a minimally connected network across task conditions. In this sparse network, each node will be connected to at least one node by an edge at one of the layers of the multiplex network.

Statistical analysis

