A full-factorial regression model will test the impulses and responses of each marker position. Impulse and Response will serve as class variables indicating the locations of impulse and response variables. Statistical significance will be interpreted as evidence of the flow of nonlinearities in movement fluctuations between the corresponding pair of anatomical locations, with the flow direction from the Impulse variable to the Response variable. Statistical significance will be set at a Type I error rate of 5%.

Extraction of functional musculoskeletal modules

The Louvain algorithm will extract functional musculoskeletal modules from the entire network. Consensus clustering will be implemented to achieve a stable partition (Lancichinetti and Fortunato, 2012). Multiplex modularity analysis will identify the functional musculoskeletal modules across different task conditions---MolTi software (<https://github.com/gilles-didier/MolTi>) will be utilized to identify functional musculoskeletal modules within multiplex networks by optimizing multiplex modularity through the modified Louvain algorithm.

Comparison of functional musculoskeletal networks across task conditions

The networks will be coarse-grained to compare functional musculoskeletal networks across task conditions (Kujala et al., 2016). The functional modules estimated across task conditions will coarse-grain the binary networks and then compare the strength of the inter-

and intra-module connections across task conditions. The nodes in clustered networks represent modules, and the edges signify the relationships between modules.

D. Does this study involve the collection of blood, urine, saliva or other human biological material (HBM)?

No

DRUGS, BIOLOGIC DRUGS AND DEVICES

13. Drugs and Biologic Drugs

1. Does this research involve the use of drugs or biologics?

No

14. Devices

1. Does this research involve a medical device(s) (including an in vitro device [IVD] (assay), and medical software)?

No

CONFIDENTIALITY AND PRIVACY

15. Confidentiality and Privacy

A. Describe where research data will be stored. Check all that apply.

[contact] (secure UNMC or UNO designated cloud-based storage site)

◆ Microsoft Office 365 application (including SharePoint, OneDrive for Business, Teams or Streams) (UNMC, UNO or NU system instance) (secure UNMC or UNO designated cloud-based storage site)

Other secure UNMC or UNO designated cloud-based storage site - describe:

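### The drawing hand in the Trail Making Test is neither fixed nor recorded, so any result combined over participants by marker location would mix drawing and passive arms

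*Protocol*

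**What the plan says.** **Task.** Section 12.A describes the test: "The Trail Making Task will be presented on a projector screen and involve drawing a trail through jumbled numbers". Under Motion tracking it adds: "An RGB camera will record the laser pointer traces on the projector screen". Each participant does three trials of each of four conditions. Two of these are Trail Making conditions, so there are 3 × 2 = 6 Trail Making trials. The instructions do not mention the hand.

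**Eligibility.** Section 9 lists four inclusion criteria: capacity to consent, to "be able to stand and walk independently without an assistive device", and no self-reported neurological or limb diagnosis. Section 10 answers N/A for exclusions. Left-handers are therefore eligible, and no section records handedness.

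**Analysis.** In section 12.C, Network modeling, the nodes are a fixed set "represented in the model as (CoP, CoM, M1, M2, ..., M79". The weights are obtained one person at a time, "defining a directional weighted musculoskeletal network for each participant and task condition". Under Statistical analysis, a full-factorial regression follows: "Impulse and Response will serve as class variables indicating the locations of impulse and response variables". A significant term is read as a flow of nonlinearity between that pair of body locations. Modules are then extracted and used to compare connection strength across task conditions.

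The markers themselves are given no left or right label. Body sides are named only in the list of segments used to compute the center of mass: "left and right hand, forearm, upper arm, thigh, shank, and foot".

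**The concern.** In the Trail Making conditions one arm is probably the task effector and the other is not. For a right-hand drawer, the change from quiet stance to the test falls on the right-arm nodes. For a left-hand drawer it falls on the left-arm nodes. A step that lines participants up by marker location treats these as the same node although their roles are opposite.

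Hypotheses 1.2 and 2.2 are about how the network is organised during the test. If location-level edges or arm-node module membership are reported for the group, true drawing-arm edges would look weaker than they are, and faint edges would appear on the other arm. Nothing in 12.A prevents a participant from changing hands between trials, which would produce the same mixing within one person. The issue is separate from whether the stance trials should include an arm movement: it would remain if they did.

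**Working it through.** The protocol gives no figure on handedness, so there is none to reproduce. The check has two parts.

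**1. Does the plan combine participants by location?**
- Network estimation does not: it is done per participant and condition.
- The Impulse/Response regression does if it is fitted over participants. The text does not say so, but it is the natural reading, because section 4.A.2 bases the sample size partly on a fixed effect of Sex, which cannot be estimated within one person.
- Module extraction does if one partition is shared over participants. The text is silent on this.

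**2. How large is the mixing if it happens?**

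Inputs:
- N = 50 (section 4.A.1).
- Type I error 5% (section 12.C); two-sided testing is assumed.
- Share of left-hand drawers p: not in the documents; assumed 10%, range 5-20%.
- Illustrative drawing-arm effect D = 0.5 for a participant-level contrast with SD 1, and no effect on the passive arm: assumed.

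Formulas for nodes labelled by the majority's drawing side:
- mean on the labelled drawing-arm node = (1-p)D
- mean on the opposite-arm node = pD
- variance at either node = 1 + p(1-p)D²
- noncentrality for the drawing-arm node = (1-p)D × √(N / variance)

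Worked at p = 10%: mean 0.9 × 0.5 = 0.45; opposite arm 0.1 × 0.5 = 0.05; variance 1 + 0.1 × 0.9 × 0.25 = 1.0225; noncentrality 0.45 × √(50/1.0225) = 3.15.

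| p | Expected left-hand drawers of 50 | P(at least one) = 1-(1-p)^50 | Effect kept, 1-p | Gained by opposite arm, p | Node power, simulated | Node power, noncentral t |
|---|---|---|---|---|---|---|
| 0 | 0 | 0 | 100% | 0% | 0.936 | 0.934 |
| 5% | 2.5 | 0.923 | 95% | 5% | 0.906 | 0.905 |
| 10% | 5 | 0.995 | 90% | 10% | 0.874 | 0.870 |
| 20% | 10 | >0.999 | 80% | 20% | 0.774 | 0.776 |

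The simulation used 20,000 runs, and the noncentral t calculation agrees with it to within 0.005. The factors 1-p and p do not depend on D; the power figures do.

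**What does not change.** Exchanging left and right labels within one participant's network only renames its nodes. Modularity and between-module connectivity computed from that network stay the same. If the hand is constant for a person, it is also constant over that person's four conditions.

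**The case against.** The strongest objection is that the protocol never states the step that does the harm. Networks are built per participant, the layers of the multiplex analysis are described across task conditions, and how people are combined may be set out in a statistical analysis plan that is not shown. This stands as a limit: the mixing is conditional. A reader might infer that the plan pools arms by left and right marker labels, but the text supports only a fixed marker set with location as a class variable.

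A second objection is that no hypothesis names an arm. Modularity and between-module connectivity do not depend on side within a person, and each participant is their own control. This also stands. A reader might infer that handedness biases the condition contrasts or invalidates Hypotheses 1.2 and 2.2. The within-subjects design in section 6 does not support that. A reader might also reason from left-right asymmetry, which would shrink to 1-2p, but the protocol plans no drawing-versus-passive-arm test. Inflation of between-person variance is not a serious argument either: on the inputs above it is 0.0225 against 1, about 2%.

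Third, 79-marker motion capture would probably show afterwards which arm drew, so alignment could be decided at analysis. That is fair for the relabelling. It does not cover the instruction: one constant hand per participant cannot be imposed once the data are collected. Hand switching is not shown to be likely; it is only not ruled out.

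**Conclusion.** The point holds in a limited form. The protocol leaves the drawing hand unfixed and unrecorded, and gives no rule for aligning markers to it. If participants are combined by marker location, in the regression or in a shared module partition, drawing-arm effects at a location shrink to about 90% (95-80% for p of 5-20%), and the opposite arm gains about 10% (5-20%). For an illustrative 0.5 SD effect with N = 50, single-node power falls from about 94% to 87% (91-77%).

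The consequence is blurred group-level arm edges and arm-node module membership in the Trail Making conditions, and no more than that.

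The size rests on assumptions outside the documents: one-handed use of the pointer, the share of left-hand drawers, left-handers drawing with the left hand, no effect on the passive arm, and the chosen effect size. If everyone drew with the same hand, the mixing would not occur. Priority is optional to moderate, mainly because the remedy is cheap and one part of it must come before data collection.

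**What to change.** - **Section 12.A:** add that each participant uses the same hand in all six Trail Making trials, and that this hand is recorded.
- **Section 12.C:** add that left and right markers are relabelled as drawing side and non-drawing side, in all four conditions, before any step that combines participants by location. Midline markers, the center of pressure and the center of mass keep their labels. The marker series are displacement magnitudes without direction, so only the labels change.

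The cost is one recorded item, one sentence of instruction and one relabelling step in the analysis code. No participant is excluded and the sample size is unchanged. The downside is that group results are reported by drawing and non-drawing side instead of anatomical left and right, so the anatomical network used for comparison must be mirrored in the same way for left-hand drawers.

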Aim 2 is about unseating one of these modular networks with a perturbation and showing that the reorganization of these networks can be understood from the cascade-like interactivity across the body. Healthy adults will maintain an upright stance on an unstable surfacea balance boardin one condition and perform the Trail Making Test while maintaining an upright stance on the same unstable surface in the other. We hypothesize that destabilizing contact with the ground surface when maintaining an upright stance will produce modular networks of multiplicative interactions with increased connectivity among these modules compared to stable standing (Hypothesis 2.1). We hypothesize that destabilizing contact with the ground surface when taking part in the Trail Making Test would produce a succession of distinct, modular networks of multiplicative interactions with increased connectivity among these modules compared to stable standing (Hypothesis 2.2).

Since fewer modular networks typically exhibit sparser intra-modular and denser inter-modular connections, we expect an inverse correlation between modularity and between-module connectivity from a theoretical standpoint.

CHARACTERISTICS OF THE SUBJECT POPULATION

4. Accrual

A. Is this study conducted solely at sites under the oversight of the UNMC IRB (e.g. UNMC, Nebraska Medicine, CHMC, UNO)?

Yes

1. How many subjects will need to be consented (per group, as applicable) in order to achieve the scientific objectives of the research?

50 healthy adults; 25 men and 25 women

2. What is the statistical or other justification for the total number of subjects described above?

Sample size determination was made based on previously observed values of statistical descriptors of movement variability in older and younger adults (older: $H = 0.64 \pm 0.08$; younger: 0.76 ± 0.07 (Hunt et al., 2014; Kaipust et al., 2013; Raffalt et al., 2021; Vaz et al., 2019; Vaz et al., 2020) and the procedure outlined in Kuznetsov and Rhea (2017). The method entails generating simulated datasets with known parameters. Power Analysis conducted across 1000 simulated datasets revealed that 16 participants per group will yield 86%, 94%, and 100% power to detect a difference of 0.1, 0.05, and 0.3 in H for fixed effects of Sex and the two nestings of experimental manipulation. We will recruit $N = 25$ participants per age group to account for possible attrition, equipment failures, etc.

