What are the potential risks associated with each research procedure, intervention, evaluation and/or test? If data are available, estimate the probability that a given harm may occur and its potential reversibility.

The potential risks of standing are similar to general bouts of light physical activity, the most likely one being fatigue due to extended standing. The trials in which participants will be asked to maintain balance on a balance board run the risk of losing balance. Balancing on the balance board might pose additional risk of loosing balance and falling. We will cover all surface adjacent to the participant with thick styrofoam to prevent injury in the unlikely case of fall.

17. Risk Classification

What is the overall risk classification of the research?

- ◆ Minimal risk

Greater than minimal risk

18. Minimization of Risk

A. Describe how the subjects of the research will be monitored by the investigators and other research personnel to ensure their safety.

We will cover all surfaces adjacent to the participant with thick styrofoam to prevent injury in

the unlikely case of a fall when balancing on the balance board. Also, the study will be terminated if the participant report to have any kind of loss of balance while participating in the study.

B. Describe how the data collected will be monitored to ensure the safety of subjects. Identify who will perform the ongoing data and safety analysis, and describe the frequency of data analysis. If there is an independent Data and Safety Monitoring Board (DSMB) provide the charter, or describe (1) the composition of the DSMB membership, (2) the frequency of DSMB meetings and reports.

Collected data will be temporarily stored on an encrypted, password-protected local hard drive after data collection sessions have been completed. After being uploaded to a secure UNO Office365 server that only the listed personnel will have access to, they will be removed from the local hard drive. Hard paper copies will be stored in a lockable file cabinet within a locked room only accessible to the listed personnel. The PI will perform ongoing data and safety analysis. Data monitoring by the PI will occur every month.

C. Describe the auditing plan for research conducted. Identify who will conduct the audits and specify the audit frequency.

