The primary investigator will be in charge of auditing the research (every 2 months) if discrepancies are found between the data collection, analysis, or logging procedures.

D. Describe the specific subject withdrawal criteria.

Participants will be asked throughout the data collection period if they are experiencing any physical discomfort and will be withdrawn from the study if stated that they do experience any physical discomfort. If the subject appears to be off balance or unsteady, they will be withdrawn from the study. Participants only need to express this to an investigator if they desire to withdraw. Suppose any aspect of the research negatively impacts their health or they no longer fit the eligibility criteria at any point in the research. In that case, the participant will be taken off the study. The study does not have any treatment or intervention beyond minimal physical activity. Therefore there is no consequence to the participant for withdrawing from the protocol

E. Describe the stopping rules for the research (e.g., the specific criteria for halting or early termination of the study).

The data collection sessions will be halted for reasons including, but not limited to: injury of any kind during data collection, equipment malfunction that may put the participants in increased harm, signs of physical injury, or expression of physical discomfort. We do not expect participants falling to be common during this project. However, if any participants fall, the study session will be terminated.

F. Describe plans and resources available to promptly address any subject injury.

The Biomechanics Research Building and the Health & Kinesiology Building have Emergency Action Plans that all investigators are familiar with. The procedures are listed in the attached document.

19. Potential Benefits to the Subject

Is there the prospect for direct benefit (eg, research on diagnosis or treatment of disease)?

No

20. Potential Benefits to Society

Describe the potential benefits to society that may reasonably be expected to result from this research.

The knowledge generated by this project will lay the foundations of a new way to understand suprapostural dexterity and its breakdown in various movement disorders.

FINANCIAL OBLIGATIONS AND COMPENSATION

22. Financial Obligations of the Subject

A. Who will pay for research procedures, interventions, evaluations and tests? Check all that apply.

Sponsor

Grant

CRC, CCTR

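### For a loss of balance without a fall, 12.A repeats the trial while 18.A terminates and 18.D withdraws, and nothing says which rule applies on the balance board

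*Protocol*

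**What the plan says.** Four places in the Protocol deal with loss of balance during a session.

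- **12.A (tasks and procedure):** a trial "will be repeated if the participants lost balance at any time between the trial for a maximum of two repetitions". The participant stays in the session.
- **18.A (safety monitoring):** "the study will be terminated if the participant report to have any kind of loss of balance while participating in the study".
- **18.D (withdrawal criteria):** "If the subject appears to be off balance or unsteady, they will be withdrawn from the study".
- **18.E (stopping rules):** "if any participants fall, the study session will be terminated". The list before it is open: "The data collection sessions will be halted for reasons including, but not limited to: injury of any kind during data collection".

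Section 16 foresees the event: "The trials in which participants will be asked to maintain balance on a balance board run the risk of losing balance". Under 12.A there are three trials in each of four conditions, in an order randomized for each participant. Two of the four conditions use the board, so 6 of the 12 trials do. Section 6.A.1 describes a within-subjects design in which everyone goes through every condition.

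**The concern.** Staff can apply the repeat rule only if they see the loss of balance or are told of it. What they see can meet 18.D, and what they are told meets 18.A. The same event can therefore call for a repeat, a termination or a withdrawal.

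Three consequences for the data follow.

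- Withdrawal on the board removes people for responding to the Aim 2 manipulation and leaves steadier people in the board data.
- Because trial order is random, a participant withdrawn on the board also loses whatever stable-surface trials were still to come, which weakens the within-person comparison behind Hypotheses 2.1 and 2.2.
- If different staff follow different sections, the retained sample depends on who ran the session.

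**Working it through.** **Setting the rules side by side, for a loss of balance without a fall**

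| Section | Trigger | Action |
|---|---|---|
| 12.A | balance lost during a trial | repeat, at most twice |
| 18.A | participant reports a loss of balance of any kind | terminate |
| 18.D | participant looks off balance or unsteady | withdraw |
| 18.E | fall, injury, discomfort, hazardous malfunction | end the session |

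The triggers are worded differently but overlap. 18.E decides the case of a fall; its open list does not decide a recoverable loss. Reading 18.A as ending only that participant's session is sensible, but still contradicts a repeat. The conflict needs no arithmetic.

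**Illustrating the consequence**

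The plan states no figure to reproduce. Inputs from 12.A: 6 board trials, 6 stable trials, random order, at most 3 attempts per trial. Assumed: p, the chance of losing balance on one board attempt, and no losses on the stable surface. One p stands in for all the triggers, although 18.D is broader than a loss of balance and 18.A covers only reported ones.

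*Equal p, independent attempts.*

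- Withdrawal at first loss, all six board trials completed: (1 − p)^6.
- Repeat rule, all six completed: (1 − p^3)^6.
- Stable trials never run under withdrawal: 6 − 6 × mean of (1 − p)^k over k = 0,…,6, because the number of board trials preceding a given stable trial is uniform on 0 to 6.

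| p | Withdrawal | Repeats | Stable trials lost, of 6 |
|---|---|---|---|
| 1% | 0.99^6 = 94% | >99.9% | 0.18 |
| 5% | 0.95^6 = 73.5% | 99.9% | 0.83 |
| 10% | 0.90^6 = 53% | 99.4% | 1.53 |

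*p varying between people.* Take p as beta(a, b) with within-person correlation 0.3 (assumed). Then a + b = 0.7/0.3 = 2.333 and a = 2.333 × mean p. Completion under withdrawal is the product over i = 0,…,5 of (b + i)/(a + b + i). Under repeats it is E[(1 − p^3)^6].

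| Mean p | Withdrawal | Repeats |
|---|---|---|
| 1% | 97% | 99% |
| 5% | 84% | 97% |
| 10% | 71% | 93% |
| 20% | 49% | 84% |

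*Selection at mean p = 5%.* Those who complete all six have mean p = a/(a + b + 6) = 0.1167/8.333 = 1.4% under withdrawal. Under repeats it is E[p(1 − p^3)^6]/E[(1 − p^3)^6] = 3.6%. Both rules select steadier people; withdrawal does so more strongly.

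**The case against.** The best defence is that the sections do different jobs. 12.A is the only rule written for running a trial, while the 18.D sentence sits among participant-level criteria such as discomfort and lost eligibility, and may mean general unsteadiness. Almost anyone on a balance board looks unsteady, so staff are unlikely to apply 18.D literally there. The specific rule would then govern. That is workable, but the reader has to supply it: the protocol does not state it, and the breadth of 18.A resists it.

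A second objection stands: p and the correlation of 0.3 have no source in the protocol, so nothing shows whether losses will be rare or common.

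Some stronger readings are tempting but not supported.

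- **A power threshold.** Section 4.A.2 says "16 participants per group will yield 86%, 94%, and 100% power" and recruits 25 "participants per age group to account for possible attrition, equipment failures, etc". One might infer that fewer than 16 completers leaves Aim 2 underpowered. That calculation concerns H and draws on values for older and younger adults. This study has one age group, and Hypotheses 2.1 and 2.2 are within-subject network comparisons, so 16 is not their threshold.
- **All six board trials are required, or partial data are lost.** The protocol says neither. 12.C defines networks per participant and condition, so fewer trials may suffice.
- **Repeats retain everyone.** Completion above 95% up to p = 20% holds only if p is equal across people; under the beta model it is 84% at mean p = 20%.
- **Falls are unregulated.** 18.E covers them.

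**Conclusion.** The contradiction holds on the text alone: for a loss of balance without a fall, the protocol gives incompatible instructions and no order of precedence. That part is firm.

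The effect on the data has a clear direction but an unknown size. Literal use of 18.A and 18.D would thin out the less steady participants and some of their stable-surface trials. The loss is small if p is near 1% (3% to 6% of participants not completing all six board trials) and substantial near 10% (29% to 47%), the range reflecting whether p varies between people. These figures are illustrations resting on an assumed p, not forecasts of attrition.

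Severity is minor to moderate. A reader might infer a safety failing, but 18.A and 18.D err toward stopping and the study is classed as minimal risk.

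**What to change.** State one rule, subject to IRB agreement.

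- **Preferred:** amend 18.A and 18.D so that a recoverable loss of balance during a trial, with no fall, injury or discomfort, is handled by the repeat rule in 12.A. A fall, injury, discomfort, or unsteadiness that staff judge unsafe ends the session.
- **Alternative:** if the IRB prefers the stricter rule, delete the repeat clause from 12.A and report withdrawals by condition.

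Either way, log losses of balance, repeats and withdrawals by condition, so that any selection can be seen.

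**Cost.** One IRB modification and a log field. The preferred option relaxes a withdrawal criterion, so it is more than a wording change; the consent text is not shown and may need to change too. Under the repeat rule, expected repeats per participant are 6(p + p^2) = 6 × (0.20 + 0.04) = 1.44 at p = 20%. With varying p they are 6 × (0.20 + 0.088) = 1.73, where 0.088 = 0.3 × 0.2 × 0.8 + 0.2^2. At seven to eight minutes a trial, that is about 10 minutes (1.44 × 7) to 14 minutes (1.73 × 8). At p = 5% and equal p it is 6 × 0.0525 = 0.32 repeats, or 2 to 3 minutes. No extra participants or visits are needed.
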